10.1.2 Secondary Endpoints

The secondary outcome measures for this trial are:

Respiratory morbidity

- Number of admissions to hospital over the 12 month trial period
- Duration of admissions to hospital over the 12 month trial period
- Time to first attack of wheeze
- Number of unscheduled GP consultations for wheeze
- Duration of episodes by diary card
- Severity of episodes by diary card
- · Parents' overall impression of efficacy of IMP

Health service use

- Unscheduled GP consultation with exacerbation of wheeze, expressed as time from randomisation to first attendance and annual attendance rate
- A&E attendance with wheeze exacerbation, expressed as time from randomisation to first attendance and annual attendance rate
- Unscheduled hospital admission with wheeze exacerbation, expressed as time from randomisation to first admission and annual rate of admissions
- Total duration of hospital admissions for exacerbation of wheeze

Adverse events

- Severe adverse events
- Withdrawal from the trial
- Mortality due to exacerbation of asthma
- Mortality due to respiratory infection
- All-cause mortality

Medication use

- Use of oral corticosteroids, expressed as number of courses taken per year, and proportion of children receiving at least one course of oral corticosteroids during the trial
- Use of inhaled relief medication (salbutamol), expressed as mean usage per wheeze episode as recorded in diary card by parent guardian.
- Use of inhaled corticosteroids (ICS), expressed as mean daily dose of beclometasone equivalent over the 12 month trial period.
- Regular prescription of inhaled ICS over the 12 month trial period

Inflammatory outcomes

Association between baseline urinary cysteinyl leukotriene level and:

WAIT Trial_ Protocol_v7_24th June 2011

Page 41 of 58

- ALOX5 status
- Other polymorphisms of leukotriene genes
- Previous history of viral-triggered episodic and multi-trigger
- Responsiveness to montelukast
- Acute history of wheeze

Genetic parameters

- Differential responsiveness to montelukast for the primary outcome in the stratum with ALOX5 promoter polymorphism [5/5], compared with the stratum with the ALOX5 [5/x + x/x] genotype.
- Differential responsiveness to montelukast for the primary outcome resulting from other polymorphisms in genes influencing leukotriene synthesis, leukotriene metabolism and leukotriene activity.

Economic outcomes

- Costs incurred by parents due to wheeze episode (including costs of travel to health care facility, childcare, and days absence from work)
- Costs of medical care provided for exacerbation of wheeze

Qualitative outcomes (parental)

- Attitudes towards genetic testing in order to personalise therapy
- Acceptability of parent-initiated therapy for preschool wheeze
- Experience of using the trial medication
- Difficulties/advantages of the parent-initiated approach
- Views on parent information sheet

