5.4 Treatment procedures

IMP will be presented as white granules administered either directly in the child's mouth, or mixed with a spoonful of cold or room temperature soft food (e.g., applesauce, ice cream, carrots and rice). The white sachet containing the granules should not be opened until ready to use. After opening the sachet, the full dose of granules must be administered within 15 minutes. If mixed with food, the granules must not be stored for future use. The granules are not intended to be dissolved in liquid for administration. However, liquids may be taken by the child subsequent to administration. The granules can be administered without regard to the timing of food ingestion. The dose is 1 sachet per day, started when the child has evidence of a viral cold or has wheeze, and stopped after 10 days. If a child vomits after the administration of the IMP no additional dose is given, and parents record this on the diary chart.

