10.1.3 Study definitions

- **1. Need for unscheduled medical attention** will be defined as an episode requiring an unscheduled attendance to either a general practitioner, or to an accident and emergency department, or a combination of both where wheeze is diagnosed by a clinician.
- **2. Time from randomisation to first attack of severe wheeze** will be defined as the number of days from the date of administration of first dose of IMP to the first date on which a wheeze exacerbation attains criteria of severity stated in 1 above.
- **3. Number of days with parent-reported wheeze** will be defined as the number of days with wheeze over the 12 month trial period obtained by telephone contact with the researcher and diary card.
- **4.** Use of inhaled relief medication, expressed as total number of occasions used over **12 month period**, and mean number per wheeze episode will be obtained from the number of actuations calculated by diary card reporting.

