10.8 Secondary endpoint analysis

A Poisson regression analysis with a random effect for individuals to allow for over-dispersion will be applied to determine the influence of allocation on number of days with parent-reported wheeze, number of admissions to hospital, number of admissions to hospital > 4 hrs duration. An incident rate ratio for each factor will be presented with 95% confidence intervals.

Time to first attack of wheeze will be analysed using a log-rank test with adjustment for clustering and, if hazards are proportional, Cox's proportional hazards models adjusting for clustering. In a Cox model, strata and centre will be included as covariates.

Other continuous variables will be analysed with analysis of covariance. Dichotomous variables will be analysed with logistic regression analysis.

Adverse events will be analysed with descriptive statistics.

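### Section 10.1.2 lists salbutamol use only as a per-episode mean, which covers only children who have an episode; the 12-month total in 10.1.3 should be the between-arm endpoint

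*Protocol*

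**What the plan says.** The secondary endpoint list (Protocol 10.1.2, Medication use) gives salbutamol as "Use of inhaled relief medication (salbutamol), expressed as mean usage per wheeze episode as recorded in diary card by parent guardian". Under respiratory morbidity the same list has "Duration of episodes by diary card" and also, as a separate item, "Severity of episodes by diary card", with no summary measure for either. The other medication endpoints in the list are defined per child: oral steroid courses per year or any course, and inhaled steroid dose or regular prescription over the 12 months.

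The definitions (10.1.3 item 4) give salbutamol two forms. One is a total for the whole year of follow-up, in wording that begins "Use of inhaled relief medication, expressed as total number of occasions used over". The other is the per-episode figure, in wording that runs "and mean number per wheeze episode will be obtained from the number of actuations calculated by diary card reporting". For parent-reported wheeze days, item 3 sets a count, taken from calls and diary cards, that "will be defined as the number of days with wheeze over the 12 month trial period obtained by telephone contact with the researcher and diary". Section 10.8 plans a Poisson regression with a random effect that "will be applied to determine the influence of allocation on number of days with parent-reported wheeze, number of admissions to hospital". Wheeze days do not appear in the 10.1.2 list. Section 10.8 sends other continuous variables to analysis of covariance.

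Trial medication is "started when the child has evidence of a viral cold or has wheeze, and stopped after 10 days" (5.4; 6.5 agrees on when it starts), so it can begin before any wheeze.

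**The concern.** Whether a child has a wheeze episode, and how many, is decided after randomisation, and changing it is the aim of the treatment. A child without an episode has no per-episode mean and leaves the comparison. The children who remain are those in whom treatment did not prevent every episode, and their episodes may differ in kind between arms. The comparison is then not protected by randomisation.

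Two errors are possible. The endpoint can show no effect on rescue use when use per child has fallen. If milder episodes are the ones prevented, it can show an increase. Sections 10.1.2 and 10.1.3 also do not match, and nothing says which salbutamol measure is the between-arm comparison.

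**Working it through.** **Inputs from the protocol.** Control attack rate 0.76 with SD 1.22, and a 33% reduction (10.2.1). Episode rates of 2.34 on placebo and 1.60 on daily montelukast (1.4.2). Target 1300 children with 6% loss (10.2.1), allocated 1:1 (5.5). The protocol gives no figure for the per-episode endpoints.

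**Step 1. The plan's treated rate.** 0.76 × (1 − 0.33) = 0.509, which agrees with the stated 0.51.

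**Step 2. Children without an episode.** Assume a negative binomial count with variance m + αm².

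α = (1.22² − 0.76) / 0.76² = 0.7284 / 0.5776 = 1.261, and 1/α = 0.793.

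P(0) = (1 + αm)^(−1/α).

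| Rate source | Control m | P(0) | Treated m | P(0) |
|---|---|---|---|---|
| Steroid-course proxy, 10.2.1 | 0.76 | 0.587 | 0.509 | 0.675 |
| Earlier trial, 1.4.2, same α (assumed) | 2.34 | 3.951^(−0.793) = 0.34 | 1.60 | 3.018^(−0.793) = 0.42 |

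The share contributing to a per-episode mean is therefore about 41% and 33% at the lower rates, and about 66% and 58% at the higher.

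**Step 3. How the two measures relate.** Use per child-year = episodes per child-year × mean use per episode. So the per-child ratio is the episode rate ratio times the per-episode ratio. With a rate ratio of 0.67, the per-child total falls whenever the per-episode ratio is below 1 / 0.67 = 1.49. Any per-episode ratio between 1.00 and 1.49 would look null or harmful while total use fell.

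**Step 4. Scenarios.** Assumed, not in the documents: a mild episode uses 10 actuations, a severe one 40, and 50% to 70% of episodes are mild.

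Worked case, 60% mild and only mild episodes prevented:
- Control per episode: 0.6 × 10 + 0.4 × 40 = 22.
- Treated per episode: (0.27 × 10 + 0.40 × 40) / 0.67 = 18.7 / 0.67 = 27.9, ratio 1.27.
- Per child-year: 0.76 × 22 = 16.7 against 0.509 × 27.9 = 14.2, ratio 0.85.

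| Which episodes are prevented | Per-episode ratio | Per-child ratio |
|---|---|---|
| Unrelated to severity | 1.00 | 0.67 |
| Unrelated, and 10% less use in the rest | 0.90 | 0.60 |
| Mild only | 1.23 to 1.30 | 0.83 to 0.87 |
| Mild only, and 10% less use in the rest | 1.11 to 1.17 | 0.74 to 0.78 |
| Severe only | 0.53 to 0.70 | 0.37 to 0.47 |

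In the last row with 70% mild, only 30% of episodes are severe, so the reduction stops at 30%.

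**Step 5. Sampling variation.** A simulation used 1300 × 0.94 / 2 = 611 children per arm and 1000 runs. It took the proxy rate, 60% mild, 55% of mild episodes prevented (0.60 × 0.55 = 0.33 of all), 10% less use in the remaining episodes, and lognormal variation in use (log SD 0.5). The mean ratio was 0.77 per child-year and 1.15 per episode. About 252 control and 198 treated children contributed to the per-episode comparison. Total use was significantly lower in 63.5% of runs, and per-episode use significantly higher in 46.7%.

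**The case against.** Much can be said for the plan as it stands.

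- **Salbutamol.** A reader might infer that the plan has only the per-episode measure. It does not: 10.1.3 item 4 defines the 12-month total. The fault is that the endpoint list leaves it out.
- **Duration and severity.** A reader might infer that these are equally exposed, with no whole-child counterpart. For duration this is not supported, because wheeze days over 12 months are defined in 10.1.3 item 3 and analysed in 10.8. Neither diary item states a summary measure, and such detail may properly sit in an SAP. The protocol defines no diary severity score that could be totalled.
- **Most children lost.** A reader might infer this from the 59% and 67%. Those figures rest on oral steroid courses used as a proxy, and diary wheeze episodes need not involve steroids. The rates in 1.4.2 leave a majority contributing. Entry requires at least two attacks, the latest within 3 months (4.1). The minimum supply in 5.3 is 2600 × 50 / 1300 = 100 sachets per child, or ten 10-day courses, though colds count towards those.
- **Reversal.** A reader might expect it. It needs preferential prevention of milder episodes, and no figure in the protocol supports that.
- **A legitimate question.** Treatment also starts once wheeze is present, and whether it then softens the episode is worth asking.
- **Other endpoints.** The primary endpoint, attendance rates and steroid courses are counted per child and would show a fall in burden.

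All of this stands and limits the point. It does not remove it: the only salbutamol measure in the endpoint list is conditional on having an episode.

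**Conclusion.** The point holds for salbutamol. Section 10.1.2 lists only the per-episode mean and does not match 10.1.3 item 4. That mean is not a comparison of all randomised children. With prevention unrelated to severity it reads 1.00 while use per child falls by about a third. With mainly mild episodes prevented it can read 1.23 to 1.30 while use per child falls by 13% to 17%. Masking needs only that episodes are prevented without regard to severity. Reversal is possible but not predicted, and both sets of ratios rest on assumed scenarios.

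The share of children outside the comparison runs from about 34% and 42% to about 59% and 67% (control and treated). This depends on which rate is closer to diary wheeze episodes and on a common negative binomial dispersion. For duration, the gap is only that wheeze days are missing from the 10.1.2 list. For severity, the documents support no more than labelling a per-episode result as conditional. These are secondary endpoints, and the primary analysis and sample size do not change.

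**What to change.** 1. In 10.1.2, make the 12-month total of salbutamol use per child (10.1.3 item 4) the between-arm endpoint, analysed as a rate over the follow-up time with diary data. State the unit, since item 4 speaks of both occasions and actuations.
2. Count zero only where the diary or a telephone call confirms that no episode occurred. Treat an unreturned diary as missing. Section 5.7 has nurses asking for cards not yet sent back, so the two cases must be kept apart.
3. Add parent-reported wheeze days to 10.1.2, as already defined in 10.1.3 item 3 and analysed in 10.8, as the whole-child counterpart to episode duration.
4. Report per-episode salbutamol use, duration and severity as supportive results, conditional on having an episode.

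The cost is a wording change plus a rule for missing diaries. The diary and telephone data are already planned. The drawback is that totals mix how often episodes occur with how intense they are, so the per-episode figures should stay in the report beside them.

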10.1.3 Study definitions

- **1. Need for unscheduled medical attention** will be defined as an episode requiring an unscheduled attendance to either a general practitioner, or to an accident and emergency department, or a combination of both where wheeze is diagnosed by a clinician.
- **2. Time from randomisation to first attack of severe wheeze** will be defined as the number of days from the date of administration of first dose of IMP to the first date on which a wheeze exacerbation attains criteria of severity stated in 1 above.
- **3. Number of days with parent-reported wheeze** will be defined as the number of days with wheeze over the 12 month trial period obtained by telephone contact with the researcher and diary card.
- **4.** Use of inhaled relief medication, expressed as total number of occasions used over **12 month period**, and mean number per wheeze episode will be obtained from the number of actuations calculated by diary card reporting.

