1.5.2 Benefits

A recent audit of "asthma" admission in children covering 67 hospitals during the period 1998-2005, found that 75% of 9,429 admissions were for preschool wheeze³. Since this was a secondary care-based audit, it very likely underestimates the total number of unscheduled attendances for preschool wheeze. A therapy that reduces the number of severe attacks will therefore have a major benefit to the NHS and children.

2 Study Aims and Objectives

The principal objective of this research is to determine whether intermittent treatment with oral montelukast in preschool children reduces the need for unscheduled medical attention for wheeze. Treatment (IMP) will be initiated by parents or guardians at the onset of every viral upper respiratory tract infection or wheezing episode and continued for 10 days.

3 Investigational plan

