6.5 Preparation and Administration of IMP

IMP will be prepared by Nova Laboratories Ltd, and shipped to pharmacy at The Royal London Hospital and additional sites. Administration of IMP is to be commenced by the parent or guardian at home at the onset of every viral upper respiratory tract infection or wheeze episode and continued for 10 days. Parents will be advised to store the IMP at room temperature, out of the reach of children, and instructed on when to initiate and stop treatment

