6.12 Dispensing of IMP

Research nurses or research assistants will withdraw IMP from the participating site pharmacy on behalf of study participants on production of a signed trial prescription. Parents will be supplied with their first supply of IMP sachets at visit 2 (T0) and issued with a replacement box when that supply expires or is exhausted/misplaced.

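### The endpoint named as time from randomisation to first severe wheeze attack is counted from the first IMP dose, which comes only at a later cold or wheeze

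*Protocol*

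**What the plan says.** Protocol section 10.1.3, item 2, is headed "Time from randomisation to first attack of severe wheeze". The text beneath it says that the measure "will be defined as the number of days from the date of administration of first dose of IMP to the first date" of a qualifying attack. For what qualifies it refers back to item 1: the clock stops once "a wheeze exacerbation attains criteria of severity stated in 1 above". Item 1 is an unscheduled GP or A&E attendance at which a clinician diagnoses wheeze.

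The first dose is a separate, later date:

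- Section 3.1 (schema) puts randomisation at −1 week and supply of IMP to parents at week 0. Section 6.12 likewise ties the first supply to Visit 2.
- Section 2: "Treatment (IMP) will be initiated by parents or guardians at the onset of every viral upper respiratory tract infection or wheezing episode".
- Section 5.4: the daily sachet is "started when the child has evidence of a viral cold or has wheeze, and stopped after 10 days".
- Section 6.5: "Administration of IMP is to be commenced by the parent or guardian at home at the onset of every viral upper respiratory tract infection", or of a wheeze episode.

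Section 10.1.2 uses randomisation as the origin for closely related endpoints, for example "Unscheduled GP consultation with exacerbation of wheeze, expressed as time from randomisation to first attendance and annual attendance rate". The A&E and admission endpoints are worded in the same way. That section also lists a time to first wheeze attack without stating an origin, and section 10.8 analyses it by log-rank test and, if hazards are proportional, Cox regression.

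**The concern.** In many trials the first dose falls on or close to the day of randomisation, and the choice of origin hardly matters. Here the first dose is triggered by the disease, by way of a parent's decision. An origin set at that point is a post-randomisation event. It is also the start of an episode that may lead to the attendance being timed.

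At stake is what this endpoint estimates. Counted from randomisation, it compares the whole randomised groups on how long children stay free of a qualifying attack. Counted from the first dose, it covers only children who were dosed, discards their time before that dose, and partly measures the days from symptom onset to attendance within one episode. Results would not line up with the GP, A&E and admission endpoints, although the events are nearly the same.

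**Working it through.** No stated figure depends on this definition, so there is none to reproduce. The check is textual, followed by an illustration of scale.

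**Step 1: the two clocks.** Let R be the date of randomisation, D the date of first dose and A the date of the first qualifying attendance.

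- Heading of item 2, and section 10.1.2: time = A − R.
- Text of item 2: time = A − D.
- The two differ by D − R. On the section 3.1 schedule IMP is supplied about one week after randomisation, so D − R is at least about a week. Beyond that it depends on when the first treated cold or wheeze occurs.

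**Step 2: what the text of item 2 yields for each type of child.**

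| Child | From randomisation | As item 2 is written |
|---|---|---|
| Dosed, attends later in the same episode | A − R | A − D, a few days |
| Dosed, first attends in a later episode | A − R | A − D, with the time from R to D lost |
| Attends before any dose, dosed later | A − R | Negative |
| Attends, never dosed | A − R | Undefined |
| No attendance, never dosed | Censored at end of follow-up | Undefined |

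Section 5.5 foresees children who take no dose. It lets their randomisation number be reassigned only if the medication has not been dispensed, so children supplied with IMP who never use it remain randomised. No passage says how the last three rows are handled.

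**Step 3: illustration of scale.** The protocol gives neither the number of colds or wheezes per child nor the share in which parents start IMP. Assume λ = 2 to 6 triggers a year, with IMP started in a share p = 0.5 to 0.9 of them.

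Share of children with no first dose in 12 months:

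- No variation between children in trigger rate: exp(−λp). This runs from exp(−2 × 0.5) = 0.37 to exp(−6 × 0.9) = 0.005.
- Gamma variation with shape k: (1 + λp/k)^(−k). Section 10.2.1 gives mean 0.76 and SD 1.22 for steroid courses, a proxy for attacks. Borrowing k from these, k = 0.76² / (1.22² − 0.76) = 0.5776 / 0.7284 = 0.793. The share then runs from (1 + 1/0.793)^(−0.793) = 0.52 to (1 + 5.4/0.793)^(−0.793) = 0.20.

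A simulation with the gamma variation, 0.76 attended attacks a year on placebo and attendance 0 to 5 days after onset gave:

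- first attack before any dose: about 3% to 36% of placebo children with an attack;
- first attack within 10 days of the first dose: about 23% to 57% of the same children;
- median time to first dose, among children dosed: about 49 to 119 days.

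The share without an origin moves from under 1% to over 50% with the assumptions. These figures show only that the issue need not be trivial.

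**The case against.** The strongest reply concerns consequence, since nothing in the protocol reconciles heading and text.

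- **Bias.** A reader might infer that a first-dose origin biases the comparison between arms. The documents do not support that. Parents and research staff are blinded (section 6.10), and the first-dose date precedes any exposure to active drug, so it should not depend on allocation. Never-dosed children and attacks before the first dose should arise equally often in both arms. This stands.
- **Reach.** A reader might also infer that the log-rank and Cox analyses in section 10.8 will certainly run from first dose. Section 10.8 assigns them to the time to first wheeze attack. The severe-attack measure of item 2 is not itself in the section 10.1.2 list and has no named analysis. The link is an inference: item 2 is the only definition an analyst could borrow for the listed endpoint. This also stands as a limit.
- **Importance.** At most one secondary time-to-event measure is touched. The GP, A&E and admission endpoints already run from randomisation, and the primary endpoint is a 12-month count. This stands.

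One reply does not stand: that the matter can be left to a statistical analysis plan. The protocol does not leave the origin open. It fixes one that conflicts with its own heading.

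**Conclusion.** The definition is wrong as written and should be corrected. Item 2 contradicts its heading and the origin used in section 10.1.2. It leaves some randomised children without a time, can give negative times, and lets the episode that prompted dosing be the event. The result would not be an intention-to-treat comparison from randomisation. Section 10.7 takes the intention-to-treat approach for the primary endpoint, and section 10.8 states no departure from it.

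The damage is a changed estimand and an incomplete analysis set for one secondary measure. Neither an error in the primary result nor a spurious treatment effect is shown. The textual contradiction rests on no assumption. The expectation of no large between-arm bias rests on blinding holding. The share of children affected cannot be stated from the protocol.

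**What to change.** In section 10.1.3, item 2, replace the first-dose date with the date of randomisation as the start of the count. State the same origin for the listed time to first wheeze attack. Add that every randomised child is included whether or not IMP was taken, and that children without an event are censored at 12 months or at last available follow-up.

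Use one origin only. The date of IMP issue at Visit 2 falls a week later on the section 3.1 schedule and would leave item 2 at odds with section 10.1.2. If time from first dose is of interest, label it supplementary and say how never-dosed children and attacks before the first dose are treated.

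The cost is a few sentences and no new data, because the randomisation date is known for every child. It is also the firmer date: the calls in section 5.7 ask whether IMP was started and for how many days, while the date of first dose depends on parents' records.
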